#### Primary analysis.

We will test the primary hypothesis that subjects who received Naloxegol 25 mg given once in the morning every day will have lower volume of residual urine in bladder when compared to placebo. We will compare the randomized groups on the volume of residual urine in bladder, which will be measured twice per day for up to 3 days (i.e., a maximum of 6 measurement times in total), using a linear mixed model adjusting for the within-subject correlation (using an autoregressive correlation structure). At each measurement time, the average of the measurements will be analyzed. Any imbalanced baseline characteristics and volume of residual urine in bladder prior to the procedure will be included as covariates in the model. If the group-by-time interaction is non-significant (P > 0.20), we will assess the group difference on the volume of residual urine across over all the measurements. In the presence of a group-by-time interaction, the group difference will be assessed separately at each measurement time and a Bonferroni correction will be made for multiple comparisons to maintain the hypothesis-wise 2-sided type I error at 0.05 (the significance criterion will be 0.05 / 6).

Second, we will assess the treatment effect within chronic opioid users and nonusers using the same statistical methods as above. The significance level will be 0.025 for each of the two subgroup analyses (Bonferroni correction).

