#### 2. STUDY DESIGN and METHODS

#### A. Study Overview

We propose to assess the effect of Naloxegol on reversing opioid-related side effects in patients recovering from elective primary hip surgery under spinal anesthesia who will be randomly assigned to oral Naloxegol or placebo for two postoperative days or until the date of discharge, whichever occurs earlier (**Table 1**). The design will be a randomized, double-blind, placebo-controlled trial of oral Naloxegol in adults having elective primary hip or knee surgery under spinal anesthesia. The study will be performed at the Cleveland Clinic hospitals.

	Preopera tive visit	Morning of surgery	During surgery	PACU*	POD** 1	POD 2	Day of discharge	
Screening for eligibility	Х	Х						
Consenting	Х							
Baseline medical, demographics, Apfel score, Patient functionality and drug history	Х	х						
Pertinent blood studies (laboratory)	Х				Х	х		
AE/SAE collection		Х			Х	Х		
Study drug (in morning, 1 hr before or 2 hr after meal)		Х			х	х		
Bladder scan at least 2 hours after study drug (morning)					х	Х		
Bladder scan (evening)				Х	х	Х		
Intraoperative record data collection			Х					
Opioid–Related Symptom Distress Scale (ORSDS)					х	х	Х	
Opioid complications survey***				X	х	Х	х	
Numerical pain score				Х	Х	Х	Х	Х
Quality of recovery survey							Х	

Table 1: study flowchart.(Detailed information will be in the CRF's)

\* PACU = post-anesthesia care unit

\*\* POD = post-operative day

\*\*\* Opioid complications survey includes nausea, vomiting, itching, ileus, anti-emetic use, antipruritic use, anti-opioid use

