In the PACU and postoperative periods, patients will be managed at the discretion of the primary care team and the staff anesthesiologist. The need for straight catheterization in PACU and/or on the floor when it is medically indicated (volumes exceeding 400 ml) will be recorded by the study team and subsequent bladder scan will therefore not be done. Postoperatively, all patients will be given intravenous or oral opioids for pain control. Clinicians will adjust analgesic management as necessary in an effort to adjust verbal response pain scores to less than 4.

Clinical evaluators for the outcomes will be blinded to group allocation and Pharmacy personnel not involved in evaluations will prepare the study drugs. Clinicians including nurses will be blinded to monitoring and will be required to perform their standard of care management after surgery.

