#### **Enrollment procedures**

The following events will occur in order:

- 1. Screening for eligible patients
- 2. Informed consent
- 3. Randomization

- 4. Administration of study drug starting the morning of surgery and for 2 additional mornings
- 5. Collection of data
- 6. Completion of CRF information

The treatment periods extends from the morning of surgery until the earlier of POD 2 or hospital discharge. Study personnel will follow the study subject until the earlier of POD 2 or hospital discharge. In the case of an adverse event, the study subject will be followed until the resolution of the event.

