#### Secondary and exploratory analysis.

We will test the following three secondary hypotheses: subjects who received Naloxegol 25 mg given once in the morning every day will have (1) fewer opioid-related side effects, (2) less need of indwelling catheterization determined by the residual volume to be above 400 ml, and (3) improved quality of recovery as compared to placebo.

The two groups will be compared on the incidence of any opioid-related side effects using a logistic regression. The frequency, severity, and bothersomeness for each of the 12 opioid-related side effects on POD 1 and 2 will be summarized. We will compare the two groups on incidence (any versus none) of need for indwelling urinary catheterization (defined as residual urine volume > 400 ml) using logistic regression. The two groups will also be compared on the Quality of Recovery scale measured on POD 2 (or day of discharge if it occurs earlier) using a linear mixed model with an autoregressive correlation structure. All the analyses will be adjusted for imbalanced baseline characteristics, if any. The hypothesis-wise 2-sided type I error for each of the secondary outcome will be controlled at 0.017 (i.e., 0.05/3, Bonferroni correction).

In addition, we will summarize the following exploratory outcomes, including satisfactory of the quality of recovery (a subjective 100-point scale) and length of hospital stay after surgery.

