#### H. Sample Size Considerations

The sample size consideration was based on the test for the primary hypothesis that patients who received Naloxegol 25 mg given once in the morning every day will have lower volume of residual urine in bladder when compared to placebo. We would need 62 patients per group [56] to have 90% power at a 2-sided alpha level of 0.05 to detect an effect size of 0.4 or more. The effect size estimation of 0.4 was very conservative as compared to the mean difference of 120 ml (SD: approximate 60 ml) in the volume of residual urine observed by Jose Carlos, I. T., et al [57]. The effect size is the difference in means of the two randomized groups divided by the pooled standard deviation. A maximum of six measurements are planned, twice per day for 3 days. However, we assumed 4 measurements per patients with a correlation of 0.3 to be conservative for the sample size calculation. Considering a loss of follow-up rate of 10%, we will need 12 more patients to reach the planned power with an end sample size of 136. A blinded data quality check will be conducted at 50% (68 patients) of the planned enrollment of 136 patients. In addition to the 136 patients, we will enroll 2 pilot patients to test feasibility of recruitment, protocol adherence, randomization process, and data collection.

SAS software version 9.4 for Windows (SAS Institute, Cary, NC) will be used for all statistical analyses and graphics.

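### The primary mixed model names only an autoregressive correlation, while the sample size implies a constant correlation of 0.3; if that holds, the overall group test has a type I error of about 8% (4 scans) or 10% (5 scans), not 5%

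*Combined protocol and SAP*

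**What the plan says.** The Primary analysis section (Data Analysis) analyses the repeated bladder scans "using a linear mixed model adjusting for the within-subject correlation (using an autoregressive correlation structure". No random intercept, empirical standard error, alternative structure or fallback is named. If the group-by-time interaction has P above 0.20, one overall group difference is tested. The chronic-opioid subgroup tests use the same methods.

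Sample Size Considerations asks for 62 patients per group "to have 90% power at a 2-sided alpha level of 0.05 to detect an effect size of 0.4 or more", and adds that "we assumed 4 measurements per patients with a correlation of 0.3 to be conservative for the sample size calculation". It defines the effect size in standard deviation units: "The effect size is the difference in means of the two randomized groups divided by the pooled standard deviation".

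The number of scans per patient varies within the plan:
- The Primary analysis section allows up to six.
- Table 1 (Study Overview) marks at most five: POD 1 and POD 2 in the row "Bladder scan at least 2 hours after study drug (morning", and PACU, POD 1 and POD 2 in the evening row.
- Series can be shorter. After catheterization a "subsequent bladder scan will therefore not be done" (Protocol section), and Enrollment procedures states: "Study personnel will follow the study subject until the earlier of POD 2 or hospital discharge".

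A smaller point: the Secondary and exploratory analysis section compares Quality of Recovery "using a linear mixed model with an autoregressive correlation structure", although it is measured once per patient.

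**The concern.** Patients usually differ from one another in a way that persists across their scans. That persistence is what a constant correlation describes, and it limits how much extra scans on the same patient can tell us about a group difference. AR(1) alone has no such component: a lag-1 correlation of 0.3 becomes 0.09 at lag 2 and 0.027 at lag 3. If the correlation does not fade, the model treats distant scans as nearly independent, overstates the information and reports too small a standard error.

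The sizing and the analysis therefore appear to rest on different correlation models, and the one behind the sizing is the one under which the analysis model fails. At stake is the 5% error rate of the primary test, which the plan otherwise protects with a Bonferroni correction for the time-specific tests. The two subgroup tests would inherit the problem.

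**Working it through.** **Inputs.** Effect size 0.4, two-sided alpha 0.05, 90% power, four measurements, correlation 0.3 and 62 per group (Sample Size Considerations); 1:1 allocation (Protocol section); autoregressive structure (Primary analysis).

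**Step 1: reproduce 62 per group.** With V the variance of a patient's average relative to a single scan,

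n per group = 2(1.960 + 1.2816)² × V / 0.4² = 131.34 × V.

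- Constant correlation 0.3, four scans: V = (1 + 3×0.3)/4 = 0.475, so n = 62.4. Power at 62 is 89.8%.
- AR(1) 0.3, equal weights: V = [4 + 2(3×0.3 + 2×0.09 + 0.027)]/16 = 0.388, so n = 51.0.
- AR(1) 0.3, generalized least squares: V = 1.3/(4 − 2×0.3) = 0.382, so n = 50.2.

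Of the structures tried, only constant correlation matches the stated 62.

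**Step 2: fit AR(1) when the truth is constant 0.3.** In large samples the AR(1) likelihood fit settles at a lag-1 correlation of 0.3. With m scans:

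- The model reports a variance factor of 1.3/(m − 0.3(m−2)).
- The weights are proportional to 1 for the first and last scan and 0.7 for those between. The true variance factor is 0.3 + 0.7 × Σw²/(Σw)².
- Type I error = 2[1 − Φ(1.96 × √(reported/true))].

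| Scans | Reported | True | SE ratio | Type I error |
|---|---|---|---|---|
| 4 | 1.3/3.4 = 0.382 | 0.3 + 0.7×2.98/3.4² = 0.480 | 0.892 | 8.0% |
| 5 | 1.3/4.1 = 0.317 | 0.3 + 0.7×3.47/4.1² = 0.445 | 0.845 | 9.8% |
| 6 | 1.3/4.8 = 0.271 | 0.3 + 0.7×3.96/4.8² = 0.420 | 0.803 | 11.6% |

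By the same formula, two scans give no inflation and three give 6.4%.

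**Step 3: simulation.** Normal data with no treatment effect, 62 per arm, REML fit with time and group effects, t test on 122 df. There were 40,000 trials per setting, and 16,000 for random intercept plus AR(1).

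| True correlation | Model fitted | 4 scans | 5 scans |
|---|---|---|---|
| Constant 0.3 | AR(1) alone | 7.8% | 9.6% |
| Lag-1 0.30, half of it constant (assumed) | AR(1) alone | 6.1% | 7.0% |
| Lags 0.40/0.25/0.21 (assumed) | AR(1) alone | 6.3% | 7.1% |
| AR(1) 0.3 | AR(1) alone | 4.9% | 5.0% |
| Constant 0.3 | Random intercept plus AR(1) | 5.0% | 5.3% |
| Constant 0.3 | Compound symmetry | 5.0% | 5.0% |

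Six complete scans with constant 0.3 give 11.3%. A separate simulation of 10,000 trials per setting gave 8.1%, 9.5% and 11.0% for four, five and six scans.

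**Step 4: sensitivity.**
- Incomplete series with constant 0.3, using assumed shares of patients with 2/3/4/5 scans (16,000 trials each): 8.4% (10/20/30/40%), 7.7% (25% each) and 7.2% (40/30/20/10%). With half-constant correlation the range is 5.7% to 6.6%.
- Adjusting for a pre-procedure scan with the same 0.3 correlation leaves (0.3 − 0.09)/(1 − 0.09) = 0.231 between the later scans. The formula then gives 7.7% (four scans) and 9.2% (five); simulation at that residual correlation gives 7.1% and 9.4%.
- Constant correlation 0.5: 8.3% and 10.1% by formula.
- Among simulated trials whose interaction P exceeds 0.20: 8.1% and 9.6%.

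Apart from that last line, the figures describe the overall group test without the interaction step.

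**The case against.** The strongest reply is that the inflation depends on how a short phrase is read. A mixed model often carries a random patient intercept; if one was intended, the test holds its level. Model-based standard errors are also an assumption. This stands as a condition on the result. But the text gives the autoregressive structure as the means of handling within-subject correlation and names nothing else, so a programmer following it could fit AR(1) alone.

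Second, the 0.3 was chosen to be conservative for sizing, not as a claim about how residual volumes behave. The word constant does not appear; it is inferred from reproducing 62. The formula is attributed to reference 56, but the supplied list ends at 53, so it cannot be checked. All of this is fair. The true pattern is unknown until the data are seen, which is a reason to choose a model valid under both patterns.

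Third, five scans may be too many. The Measurements section places scanning in the ward twice daily, which over POD 1 and POD 2 gives four, and discharge or catheterization shortens the series. Fewer scans do reduce the problem. Even so, Table 1 marks five, the Primary analysis section allows six, and the four-scan planning case already gives about 8%.

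Fourth, the planned adjustment for pre-procedure residual volume absorbs part of the patient component. It does, but only down to about 7.7% and 9.2%, and Table 1 schedules no pre-procedure scan.

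**Conclusion.** The concern holds as a conditional statement about the primary test. With AR(1) alone, model-based standard errors, 62 per arm, complete series and a constant correlation of 0.3, the overall group test has a type I error of about 8% with four scans and about 10% with five. From the main simulation, that is 7.8/5 = 1.6 times and 9.6/5 = 1.9 times the nominal rate. The large-sample formula and the simulations agree closely.

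With partly decaying correlation and complete series the rate is about 6% to 7%. If the correlation truly decays as AR(1), or if a random intercept is also fitted, there is no material inflation. The plan does not say which model is meant, and the AR(1)-only reading is the one that its own sizing assumption undermines. This should be fixed before unblinding. The Quality of Recovery wording is a minor matter that does not affect error rates.

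**What to change.** Before unblinding, replace AR(1) alone with a structure that allows a stable patient-level component. Any of these would serve:
- a random patient intercept plus AR(1);
- an unstructured covariance with Kenward-Roger degrees of freedom (five scan times give 15 parameters);
- compound symmetry with empirical (sandwich) standard errors.

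Name one as primary and give a fixed fallback order triggered only by non-convergence. If a random intercept was always intended, one clarifying phrase is enough. The unstructured option was checked only through a t test of patient means (5.0% with four and with five scans). On complete data the two coincide when the group effect is averaged equally over scan times.

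For Quality of Recovery, use ordinary linear regression, since each patient contributes one value.

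The cost is SAP wording and about one line of SAS code, with no added patients. If the correlation is constant at 0.3, the reported standard error will be wider than AR(1) would show, by √(0.475/0.3824) = 1.11 with four scans and √(0.440/0.3171) = 1.18 with five, where 0.440 = (1 + 4×0.3)/5. That is its correct width. Simulated power at effect size 0.4 (8,000 trials) is 89% and 91%, in line with the planned 90%. If AR(1) is true, even an equal-weight analysis loses under 1% in standard error: √(0.388/0.382) = 1.008.

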#### A. Primary Aim

To assess whether patients who received Naloxegol have a lower volume of residual urine in bladder.

Hypothesis: Our primary hypothesis is that patients who received Naloxegol 25 mg given once in the morning every day will have lower volume of residual urine in bladder when compared to placebo.

Post-void residual volume will be measured after asking patient to urinate independent of their previous urination. Post-void residual is a measurement of the urine that remains in the bladder less than 30 minutes following voiding that identifies urinary retention.

Ultrasound has been used as an imaging modality to evaluate bladder function, and its use in the perioperative period as a diagnostic tool for POUR has gained popularity in the past decade. Several studies have shown good correlation between the volumes measured by bladder catheterization and by ultrasound.

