#### F. Measurements

Data will be recorded on a case report form (CRF) which will be available electronically and on paper format.

Demographic data to be obtained includes height (cm), weight (kg), age (yr), gender, physical status (ASA), and self-declared ethnicity. Patients will be questioned for social history (tobacco) and medical history (pulmonary disease, kidney disease, diabetes mellitus, neurological disease, chronic pain conditions, illegal drug usage, alcohol abuse, myocardial infarction, previous surgery or stent placement and medications usage). Available preoperative laboratory tests and medication list will be recorded. Individual risk for nausea and vomiting will be determined using the Apfel score.

Data obtained from electronic medical records will include: operation time, surgery type, intraoperative opioid consumption, postoperative opioid consumption in PACU and in ward,

breakthrough pain medication requirements, pain scores in PACU and ward, requirement of oxygen in PACU and ward, nausea and vomiting, requirement of antiemetics, pruritus, requirement of antihistaminic medications, ambulation time, flatus, ileus, bowel movements, constipation, length of stay and any side effects or complications. Preoperative and postoperative laboratory data including but not limited to liver function and coagulations test results will also be collected from electronic medical records. Patient functionality will also be recorded including bathing, toileting, walking and moving.

The Residual volume will be measured within 30 minutes after urination using the batterypowered, portable Bladder scan™ BVI 3000® (Verathon, Bothell, WA, USA). The scanner will be placed on the suprapubic area and held stationary during measurement scanning. The diameter of the bladder and volume of urine will be calculated from the scan data. Scans will be repeated several times to ensure accuracy in measurements. The average of the measurements at each measurement time will be analyzed. All clinical procedures will be performed by trained MD research fellows in the ward twice daily. Surgical team will be blinded to volume determined by scanning and we will also record if they had ordered indwelling catheterization.

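### The primary model requires a pre-procedure residual volume that the visit schedule does not show, and no full-sample model names the stratification factor

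*Combined protocol and SAP*

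**What the plan says.** **Model.** The Primary analysis section compares the arms with a linear mixed model and states: "Any imbalanced baseline characteristics and volume of residual urine in bladder prior to the procedure will be included as covariates in the model". The condition of imbalance attaches to the baseline characteristics; the pre-procedure volume enters regardless. The outcome is "measured twice per day for up to 3 days (i.e., a maximum of 6 measurement times in total").

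**Schedule.** Table 1 (Study Overview) has two scan rows. The row "Bladder scan at least 2 hours after study drug (morning") is marked on POD 1 and POD 2. The row "Bladder scan (evening") is marked in PACU and on POD 1 and POD 2. The row for the preoperative visit and morning of surgery reads "Baseline medical, demographics, Apfel score, Patient functionality and drug history" and contains no scan. The table caption adds: "Detailed information will be in the CRF's".

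**Other sections.** The Primary Aim describes how the scan is done but not when: "Post-void residual volume will be measured after asking patient to urinate independent of their previous urination". Measurements says: "All clinical procedures will be performed by trained MD research fellows in the ward twice daily". The ordered steps under Enrollment procedures include no baseline scan. Under Protocol, study drug starts on the morning of surgery.

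**Stratification.** Under Protocol, randomisation is 1:1 and stratified by chronic opioid use. Under Data Analysis, a covariate enters the models if its standardized difference exceeds 0.2. Chronic opioid use appears in the analysis only as two subgroup analyses, each at 0.025. The full-sample primary and secondary models do not name it.

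**The concern.** A primary analysis should be executable from the plan. Here a reader cannot tell whether the required covariate is collected, whether it precedes the first dose, or what happens to a patient who lacks it. The Data Analysis section gives no rule for a missing covariate, and a mixed model fitted in the usual way drops such patients. If these choices are left open, they could be made after the arms are known.

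A separate mismatch sits beside this one. The Primary analysis and Sample Size sections count six outcome times, and Table 1 marks five. The count also sets the divisor for the per-time tests (0.05/6).

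The second and smaller part concerns design and analysis. A factor used to stratify randomisation is normally carried into the main model. The 0.2 rule will rarely bring it in, because stratification is there to keep it balanced.

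**Working it through.** **1. Model against schedule**

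| Time | Scan marked in Table 1 |
|---|---|
| Preoperative visit | none |
| Morning of surgery (first dose) | none |
| PACU | evening row |
| POD 1 | morning and evening |
| POD 2 | morning and evening |

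Table 1 therefore gives 1 + 2 + 2 = 5 scans, all after surgery, against six outcome times in the analysis text. The Primary analysis section names the pre-procedure volume separately from those six.

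**2. Reproducing the planned sample size**

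Inputs from Sample Size Considerations: effect size 0.4 SD, 4 measurements, correlation 0.3, two-sided alpha 0.05, power 90%, 62 per group.

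- Variance of a patient's mean, equal correlation: V = (1 + 3 × 0.3)/4 = 0.475.
- n per group = 2 × (1.96 + 1.2816)² × 0.475 / 0.4² = 62.4, in line with the stated 62.
- At 62 per group: SE = √(2 × 0.475/62) = 0.1238; 0.4/0.1238 = 3.231; power = Φ(3.231 − 1.96) = 89.8%.

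This calculation uses neither the baseline volume nor the stratification factor, so the planned size does not depend on either.

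**3. If the covariate is missing in some patients**

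The documents give neither the missing share nor the correlation r between baseline and each follow-up value. Assumed: 10, 20 or 30% missing; r = 0 or 0.3.

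- Residual variance = V − r²: 0.475 at r = 0, and 0.475 − 0.09 = 0.385 at r = 0.3.
- Complete cases: N = 124 × (1 − m), rounded; SE = √(4 × variance/N).
- Baseline imputation at r = 0.3 keeps N = 124, with variance (1 − m) × 0.385 + m × 0.475 = 0.394, 0.403 and 0.412.

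| Missing | N, complete case | Power, r = 0 | Power, r = 0.3 | Imputation, r = 0.3 |
|---|---|---|---|---|
| 10% | 112 | 86.7% | 92.7% | 94.4% |
| 20% | 99 | 82.3% | 89.4% | 93.9% |
| 30% | 87 | 77.2% | 85.2% | 93.4% |

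The break-even with the plan at r = 0.3 is 1 − 0.385/0.475 = 18.9% missing. With imputation and r = 0, power stays at 89.8%. Deleting the covariate also leaves 89.8%.

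**4. Stratification factor**

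*Will the 0.2 rule select it?* Take 68 per arm (136/2) and an assumed 20% users, so the SD is √(0.2 × 0.8) = 0.4. A difference of 2 users between arms gives (2/68)/0.4 = 0.074; of 5, 0.184; of 6, 0.221. The arms would have to differ by 6 users, which stratification makes unlikely.

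*Gain from including it.* Assumed: users and nonusers differ by 0.4 SD, and a share p = 10-30% are users. Between-stratum variance B = p(1 − p) × 0.4². Adjusted power = Φ(0.4/SE − 1.96), where SE = √(2(V − B)/62). Without the factor, the critical value becomes 1.96 × √(V/(V − B)).

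| p | B | V − B | Power without | Power with | Gain |
|---|---|---|---|---|---|
| 10% | 0.0144 | 0.4606 | 90.2% | 90.7% | 0.5 points |
| 30% | 0.0336 | 0.4414 | 90.6% | 91.8% | 1.2 points |

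**The case against.** **The CRFs may settle it.** Table 1 leaves detail to forms that are not part of the document. A reader might infer that no baseline value is collected and that the primary model cannot be fitted. The documents do not support that: a complete pre-dose value may be recorded. What stands is that the protocol does not show it.

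**The consequences may be nil or favourable.** This is largely right. Deleting the covariate keeps the planned power, and a moderately prognostic baseline with few missing values raises it. Losses need complete-case analysis together with either a baseline of little prognostic value or substantial missingness, and nothing in the documents predicts these.

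**A post-dose baseline.** A reader might infer that the covariate already carries a drug effect and would shrink the estimate. The plan does not say that the value is taken after the dose. A marked effect on residual volume before any opioid is given would be a further assumption. Only the timing ambiguity stands.

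**The sixth time slot.** It is tempting to read the unlocated sixth measurement as the baseline scan. The Primary analysis section counts all six as outcomes, so the mismatch is a separate discrepancy and not evidence about the covariate.

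**The stratification factor does no harm by its absence.** This stands. The 0.2 rule is pre-specified, and the factor is already used in the subgroup analyses. A reader might want to read actual type I error levels from the formula in the working. It assumes equal correlation, while the planned model is autoregressive, so absolute alpha levels from it would not describe the planned test. The power figures are illustrations with the same limit.

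**Conclusion.** Both parts hold in a limited form.

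1. The primary model requires a covariate that the protocol does not schedule, and its wording does not guarantee a pre-dose value. This is a gap in specification. It shows neither a wrong sample size nor a biased analysis. With an assumed 10-30% missing and complete cases only, power would be 86.7-77.2% if the baseline has no prognostic value. At an assumed correlation of 0.3 it would be 92.7-85.2%, with a loss against plan only above about 19% missing. The mismatch of five and six scan times also needs reconciling.

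2. Including chronic opioid use in the full-sample models is a free improvement worth about 0.5-1.2 percentage points of power, given an assumed 0.4 SD difference and 10-30% users. Its omission causes no bias and no alpha inflation, and planned power is kept.

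The textual gaps are certain. The sizes rest on the assumed inputs and on the equal-correlation reading that reproduces the planned 62 per group.

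**What to change.** Before unblinding:

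- **If a pre-dose residual volume is recorded:** enter it in Table 1, define the covariate in the Primary analysis section as pre-dose values only, and keep patients with a missing baseline in the model by simple baseline imputation.
- **If it is not recorded:** delete the covariate.
- **Scan count:** reconcile the five scans in Table 1 with the six outcome times in the Primary analysis and Sample Size sections.
- **Stratification factor:** add chronic opioid use as a fixed covariate in the primary mixed model and the quality-of-recovery model. Add it to the logistic models only where event counts allow. The 0.2 rule can stay.

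The cost is wording in Table 1 and the analysis sections. No visit or procedure is added, chronic opioid status is already recorded for randomisation, and the sample size does not change.

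### The interaction pre-test that selects the primary test breaks the stated 5% two-sided error: about 6.3–7.2% with four or five scans at the plan's own correlation of 0.3

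*Combined protocol and SAP*

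**What the plan says.** Under Data Analysis, Primary analysis, residual urine volume is compared between groups with a linear mixed model using an autoregressive within-patient correlation, with "a maximum of 6 measurement times in total". Which test is primary depends on the interaction P value:

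- "If the group-by-time interaction is non-significant (P > 0.20), we will assess the group difference" over all measurements.
- "In the presence of a group-by-time interaction, the group difference will be assessed separately at each measurement time", with a Bonferroni correction "to maintain the hypothesis-wise 2-sided type I error at 0.05 (the significance criterion will be 0.05 / 6").

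The analyses in chronic opioid users and nonusers repeat this, "using the same statistical methods as above. The significance level will be 0.025 for each of the two subgroup analyses". No by-time criterion is given for them.

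Section H, Sample Size Considerations, sizes the trial at 62 per group "to have 90% power at a 2-sided alpha level of 0.05 to detect an effect size of 0.4 or more", and adds that "we assumed 4 measurements per patients with a correlation of 0.3 to be conservative". Nothing in the document adjusts for there being two routes to rejection.

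**The concern.** The 0.05/6 criterion limits the error of the set of by-time tests taken on their own. It takes no account of the error already spent when the interaction is not significant and the overall difference is tested at 0.05. The by-time route is also not entered at random. It is entered when the group differences vary across times, and that is when one of them is likely to be extreme.

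At stake is the error rate of the trial's main claim. The rule is presented as holding 5%, and the sample size rests on that level. The hypothesis is directional, so what matters in practice is the chance of falsely claiming benefit, which should be 2.5%.

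**Working it through.** **Inputs.** From the Primary analysis: pre-test level 0.20, overall test at 0.05, by-time criterion 0.05/6 = 0.00833, at most six times, AR(1). From section H: 62 per group, effect size 0.4, four measurements, correlation 0.3. Table 1 marks at most five scans (morning on POD 1 and 2; evening in PACU and on POD 1 and 2), so four, five and six are all shown.

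**The plan's own figure.** With an exchangeable correlation, n per group = 2(1.960 + 1.282)² / 0.4² × (1 + 3 × 0.3)/4 = 131.34 × 0.475 = 62.39. Power at 62 is 89.8%. The stated 62 is reproduced, and it belongs to a single overall test at 0.05.

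**Overall route under no effect.** With known covariance, the generalised-least-squares average is independent of the interaction statistic. This route therefore rejects with probability 0.80 × 0.05 = 0.040. To hold 5%, the by-time route may use at most 0.010.

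**By-time route under no effect.** I simulated 1,000,000 trials per setting. The m group differences were normal with covariance (2/62)R, where R is exchangeable or AR(1) and is also the covariance used in the analysis. The interaction was a Wald chi-square on m − 1 df. Results at correlation 0.3, exchangeable / AR(1):

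| Scans | Overall route | By-time route | Total |
|---|---|---|---|
| 4 | 4.0% | 2.28 / 2.56% | 6.3 / 6.6% |
| 5 | 4.0% | 2.72 / 3.18% | 6.7 / 7.2% |
| 6 | 4.0% | 3.11 / 3.77% | 7.1 / 7.8% |

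**Why the by-time route spends so much.** With four exchangeable scans, some time falls below 0.05/6 in 3.15% of null trials. If entry to this route were unrelated to those hits, it would catch one fifth of them: 0.20 × 3.15 = 0.63 points, for a total of 4.6%. It in fact catches 2.28 of the 3.15 points, about 72%.

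**False claim of benefit** at correlation 0.3: 3.1–3.3% with four scans and 3.4–3.6% with five, against 2.5%.

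**Sensitivity.**

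- Finite samples (62 per arm, AR(1) true and fitted, variance and correlation estimated), range over several checks: 6.3–6.7% (4 scans), 6.6–7.2% (5), 7.2–7.8% (6).
- Half the patients missing the last two scans (an assumption), correlation 0.3: 6.4–6.6% (4), 6.9–7.2% (5).
- Other correlations (assumptions), four or five scans: 5.7–6.7% at 0.5; 5.2–6.0% at 0.7; 4.6–5.0% at 0.9.
- Three scans at 0.3: 5.8–5.9%.

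**Subgroups** at 0.3, four or five scans, against a nominal 2.5%: 3.3–3.8% if the by-time criterion is read as 0.025/6, and 4.3–5.2% if 0.05/6 is carried over.

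**The case against.** The mechanism is hard to dispute on the ordinary reading of the text, but there are fair points about size and remedy.

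- *Six scans is a ceiling.* Table 1 marks no more than five, patients may be discharged early, and after a catheterisation the "subsequent bladder scan will therefore not be done". This stands. The four- and five-scan figures are the relevant ones, and the excess falls further with three scans (5.8–5.9%) or two (5.1–5.2%).
- *The correlation of 0.3 is a planning value, not an estimate.* This also stands. At 0.7 the excess with four scans is only 0.2–0.6 points. But 0.3 is the only value the plan gives, and its stated control should hold there.
- *The plan fits AR(1), so the exchangeable figures are not its analysis.* Correct. They are the low end under a correctly specified model; the AR(1) figures are 6.6% and 7.2% for four and five scans. If the data were exchangeable at 0.3 and AR(1) were fitted with model-based standard errors, the rule would reject about 8.7–9.0%, 10.1–10.6% and 12.1–12.4% for four, five and six scans. Most of that excess comes from the wrong covariance. The overall test alone would still reject about 8.0%, 9.7% and 11.6%. This is a separate problem that the fix here does not cure.
- *For the subgroups, 0.025/6 is the natural reading.* Probably so, and then 3.3–3.8% applies. The text does not say it, and that figure is still above 2.5%.
- *The by-time tests could be mere follow-up.* The text does not support this. They replace the overall test within the primary analysis and carry a correction meant to control the error of that hypothesis.
- *A sole overall test gives up much power for time-limited effects.* True. The choice between the two remedies below is a judgement for the team.

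**Conclusion.** The concern holds. At the plan's own correlation of 0.3 and with a correctly specified model, the rule has a two-sided type I error of 6.3–7.2% with four or five scans and 7.1–7.8% with six, not 5%. The excess is modest, but it falls on the main claim and comes from a rule said to prevent it.

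The figures assume that a significant result at any one time counts as success, that an interaction is taken as present when P ≤ 0.20, and that the data are normal with no effect at any time. They do not carry over to high correlations: near 0.9 there is no excess. The rule should be changed before the data are unblinded.

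**What to change.** **Option A (preferred, because section H sized this test).** Make the two-sided 0.05 test of the average group difference the only primary test, whatever the interaction P value. Define the contrast, for example the equally weighted mean over scheduled scans from the model with group-by-time terms. Report the interaction and the by-time estimates with confidence intervals as supportive. In each subgroup, use the average test at 0.025.

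**Option B, if confirmatory claims by time are wanted.** Keep the two steps but set the by-time criterion at 0.01/6. The total is then at most 0.80 × 0.05 + 6 × 0.01/6 = 0.04 + 0.01 = 0.05 under a correctly specified model. Simulation at correlation 0.3 gives 4.6–4.9% for four to six scans. In the subgroups the matching criterion is 0.005/6, since 0.80 × 0.025 = 0.020 leaves 0.005.

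**Cost.** Neither option adds patients or procedures. Power at 62 per group, exchangeable correlation 0.3 (the two time-limited effects are my assumptions):

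| True effect | As written | Option A | Option B |
|---|---|---|---|
| 0.4 SD at all four scans | 89.9% | 89.8% | 86.5% |
| 0.6 SD at one of four | 77% | 23% | 59% |
| 0.6 SD at two of five | 92% | 52% | 78% |

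The time-limited rows deserve weight. Dosing is once daily, and the Introduction gives a half-life of 6–11 hours, so an effect that differs between morning and evening is plausible. Equal weighting also costs some power when scans are missing. If half the patients lack the last two of four scans, power for the constant effect is 82%, against 85% with the model's own weights. Neither option settles whether AR(1) fits the data; that needs its own answer.
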